### 9.4.1 Questionnaire description

The questionnaires will have a disclaimer and consent in the beginning. It collects information on demographics and eligibility of participants. It has included closed questions on the content of the EM, the question will be in order from the simplest to the hardest and from awareness to implementation. Furthermore, it is non-directing and not favouring social desirability, there is no possibility of coming back on previous answers to avoid information bias.

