#### 9.4.3 Questionnaire development

Each questionnaire i.e. prescriber, pharmacist and patient questionnaire was developed in English. The questionnaires were designed to be non-directing, clear, to avoid inducement of social desirability and had no self-evident answers. Each questionnaire included questions about screening criteria, demographics, receipt and awareness of MTX EMs, and knowledge about MTX risks. The prescriber and pharmacist questionnaire had additional questions about self-declared behaviour.

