	Q7. What helps you make treatment decisions while managing patients who have been prescribed, oral and parenteral, once-weekly methotrexate?	No; complementray information on making treatment decisions		A prescriber is successful for self-declared behaviour when all questions regarding self-declared
Self-declared behaviour (7 questions)	Q8. How would you describe your experience with the [HCP guide: country-specific name]?	No; complementary information on user friendliness of educational material		behaviour are completed with desirable answers. Success for self-declared behaviou if $\geq 80\%$ of prescribers are
	Q9. How would you describe your experience with the [HCP checklist: country-specific name]?	No; complementary information on user		successful.

Template No.: RWI\_TP\_EPI0016 Revision 1 Reference: RWI\_WI\_EPI0005

Effective Date: 15Jun2018

Page 86 of 92

Objectives	Questions	Is the question included in the assessment of success? (Yes/No)	Definition of correctly answered question	Assessment of success
		friendliness of educational material		
	Q10. How often do you provide dosing instructions and information about overdose symptoms for once-weekly, oral and parenteral, methotrexate to the patient/caregiver?	Yes	Question completed correctly [Answer '1' is desirable]	
	Q11. Please specify the reasons you choose to not inform the patient/caregiver about the dosing instructions and symptoms of overdose at each/any visit?	No; complementary information on reason for self-declared behaviour to Q10		
	Q12. How do you write down the day of the week the patient should take the once weekly dose of methotrexate, oral and parenteral, in the prescription?	Yes	Question completed correctly [Answer '1' is desirable]	
	Q13. Please specify the reasons you do not write the day of intake in the prescription at each/any visit?	No; complementary information on reason for self-declared behaviour to Q12		

Template No.: RWI\_TP\_EPI0016 Revision 1 Reference: RWI\_WI\_EPI0005

Effective Date: 15Jun2018

Protocol/Study No: SC02 EMA/2018/19/PE Page 87 of 92

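### Scored prescriber item Q12 asks how the intake day is written, not whether or how often, so its stem is leading and does not match its follow-up Q13 or the parallel item Q10

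*Protocol*

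**What the plan says.** Annex 5.1 of the protocol lists seven prescriber items under self-declared behaviour, Q7 to Q13. Five are complementary and unscored. The two scored items are:

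- Q10: "Q10. How often do you provide dosing instructions and information about overdose symptoms"
- Q12: "Q12. How do you write down the day of the week the patient should take the once weekly dose of methotrexate"

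The scoring entry for each is the same: "Question completed correctly [Answer '1' is desirable". Each scored item has an unscored follow-up, Q11 for Q10 and Q13 for Q12. The Q13 stem is "Please specify the reasons you do not write the day of intake in the prescription at each/any visit", and the table labels it "complementary information on reason for self-declared behaviour to Q12".

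A prescriber succeeds on self-declared behaviour only if every scored item has the desirable answer. The outcome succeeds if at least 80% of prescribers do (Annex 5.1; section 9.7.2.2, Assessment of success). Adherence to SmPC recommendations is part of primary objective 1.

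The protocol also sets a standard for its own wording. Section 9.4.1 says of the questionnaire that "it is non-directing and not favouring social desirability". Section 9.4.3 says: "The questionnaires were designed to be non-directing, clear, to avoid inducement of social desirability".

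**The concern.** A question that asks how someone does a thing presumes that they do it. A prescriber who seldom or never writes the intake day meets a stem that already credits them with the expected practice. The stem also asks about a manner, while the follow-up treats the answer as a frequency. Respondents may therefore read the item in different ways, and the scored answer may not mean the same thing for all of them.

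Under an all-items rule with two scored items, half of the scored content for this outcome rests on Q12. If the wording draws some prescribers to the desirable answer, the error favours concluding that the measures worked. Respondents cannot return to an earlier answer (sections 9.4.1, 9.6.1 and 9.8.1), so reaching Q13 cannot correct Q12. No later analysis can repair a question already asked.

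**Working it through.** **1. Setting the items side by side (Annex 5.1)**

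| Pair | Scored stem asks | Follow-up asks |
|---|---|---|
| Q10, Q11 | how often | why not at each or any visit |
| Q12, Q13 | how | why not at each or any visit |

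The follow-ups have the same form; the scored stems do not. Q13 is labelled as the reason for the Q12 answer, so Q12 must be meant to record whether and how often the day is written. Its stem asks neither. The nearest pharmacist item, Q9 in Annex 5.2, asks respondents to choose the option that best describes their experience, so the protocol already contains a neutral form.

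**2. What Q13 implies about the answer options**

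Q13 makes sense only if some prescribers can report not writing the day, or not at every visit. The Q12 options very probably include such answers. They are in the stand-alone prescriber questionnaire (Annex 1), which is not shown. The missing frequency term is therefore a fact about the stem, not about the whole item.

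**3. The plan's own figure**

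The point itself contains no number. The sample size it depends on reproduces: n = p(1−p)z²/e² = 0.5 × 0.5 × 1.96² / 0.08² = 150.06, against the stated 150 (section 9.5.1). The 80% threshold is 0.80 × 150 = 120 prescribers, unweighted.

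**4. How much an inflated Q12 could matter**

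All Q10 and Q12 rates below are assumptions; the documents give none. The share succeeding on both items is Q10 × Q12 if they are independent, and min(Q10, Q12) if they overlap fully. The last figure in each pair is the binomial probability of at least 120 successes in 150.

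| Q10 | Q12 | Independent: joint share, P(≥120) | Full overlap: joint share, P(≥120) |
|---|---|---|---|
| 90% | 80% | 0.90 × 0.80 = 72.0%, 0.02 | 80%, 0.55 |
| 90% | 85% | 0.90 × 0.85 = 76.5%, 0.18 | 85%, 0.96 |
| 90% | 90% | 0.90 × 0.90 = 81.0%, 0.67 | 90%, 1.00 |
| 90% | 95% | 0.90 × 0.95 = 85.5%, 0.98 | 90%, 1.00 |
| 85% | 85% | 0.85 × 0.85 = 72.3%, 0.02 | 85%, 0.96 |
| 85% | 95% | 0.85 × 0.95 = 80.8%, 0.64 | 85%, 0.96 |

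Under independence, a five-point rise in Q12 (85% to 90%, with Q10 at 90%) carries the joint share across 80%. Under full overlap, the same rise leaves it above 80% at both ends, and with Q10 above 80% the verdict turns only if Q12 itself crosses 80%. In every case the joint share is at most the Q10 rate, so Q12 cannot produce a true share of 80% when Q10 lies below it.

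**The case against.** The strongest objection is that Annex 5 is a scoring table, not the instrument. Whether an item leads depends on the stem together with its options, and the options are not shown. An explicit option for not writing the day, which Q13 suggests exists, would remove much of the pressure. The simplest explanation may be an editorial slip, such as a dropped word. This stands to the extent that a reader might infer from the stem that Q12 is biased upward and that a non-writer has no truthful answer. The documents do not support either inference. Only answer 1 scores, its wording is unknown, and a presuming stem might merely discourage the never option without moving anyone to answer 1.

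A reader might also infer that the wording alone could produce a verdict that the measures are effective. That does not follow. The flip in the table depends on assumed rates and on independence, which is doubtful for two self-reports by the same prescriber. The 80% threshold also applies separately to awareness, knowledge and behaviour.

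Q10 is not a perfect model either: asking how often also presumes something, although a frequency scale can run down to never.

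Finally, the protocol acknowledges social desirability as a limitation (section 9.9.1) and provides for piloting, translation and EMA review of the translations. Review may catch the problem, but these steps are not aimed at it. The pilot uses three prescribers to check language and medical terms (section 9.4.5). Back-translation (section 9.4.4) tests fidelity to the English and would tend to preserve a leading stem.

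These objections limit what can be said about bias. They do not remove the mismatch between the printed stem, its follow-up and the parallel item.

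**Conclusion.** The point holds as a wording defect in a scored item. As printed, Q12 presumes the practice and asks about manner, while Q13 and Q10 show that occurrence and frequency are wanted. That conflicts with the non-directing standard in sections 9.4.1 and 9.4.3, and it affects one of only two items behind the prescriber self-declared behaviour outcome.

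Upward bias is plausible; neither its existence nor its size is shown. The illustration shows only that the outcome could be sensitive to a shift of a few points in Q12 if the items are close to independent and the rates lie near the threshold. It rests on assumed rates and on unweighted counts, whereas section 9.5.3 gives precedence to weighted results where available. The correction is worth making because it is cheap and the item feeds a primary objective. Confidence is medium, since the full questionnaire could show that the options already resolve much of the problem.

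**What to change.** Reword the Q12 stem neutrally, in parallel with Q10 and Q13. For example: *How often, if at all, do you write the day of the week of intake in the prescription?* Give frequency options that include never. Check in the stand-alone questionnaire that scored answer 1 is the option for writing the day every time, so that it is consistent with Q10 and with the routing to Q13.

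The cost is one stem, with options if needed, to retranslate into the local languages of the five countries. The sample size and the 80% threshold do not change. The reported behaviour rate may come out lower.

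Timing needs checking. Protocol version 2.0 is dated 21 February 2022, while section 6 planned data collection from 1 January 2022, subject to the timeline of protocol approval. If fieldwork has already begun, report Q10 and Q12 separately beside the joint outcome and state the Q12 wording as a limitation.

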# 5.2 Assessment of Success (Pharmacist questionnaire)

Objectives	Questions	Is the question included in the assessment of success? (Yes/No)	Definition of correctly answered question	Assessment of success
	Q1. Please select the option that best describes your experience with the [patient card: name in the local language] (for oral methotrexate formulations)?	Yes	Question completed correctly [Answer '2'is desirable]	A pharmacist is successful for awareness when he/she is aware of the patient card and the visual
Awareness (3 questions)	Q2. In your daily practice, what version of the [patient card: name in the local language] related to methotrexate are you aware of?	No; complementary information related to Q1		reminder on MTX outer packaging (desirable answers).
	Q3. Please select the option that best describes your experience with the methotrexate outer packaging  Yes		Question completed correctly [Answer '1' is desirable]	Success for awareness if ≥80% of pharmacists are successful
	Q4. According to your knowledge about the [patient card: name in the local language], please indicate if you agree or disagree with the following statements	Yes	Question completed correctly [6 sub-questions; answers '1', '3' and '5' are True; '2', '4' and '6' are False]	A pharmacist is successful for knowledge when he/she scores at least 8 out of 10 points (80%) for sub-questions that are correctely answered.  Success for knowledge if ≥ 80% of
Knowledge (5 questions)	Q5. According to your knowledge about the safety measures on the outer packaging of oral and parenteral methotrexate-containing products, please indicate if you agree or disagree with the following statements	Yes	Question completed correctly [4 sub-questions; answers '1' and '3' are True; '2' '4' and '5' are False ]	
	Q6. What is your experience with the [patient card: name in the local language]?	No; complementary information on user friendliness of patient card		pharmacists are successful.

Template No.: RWI\_TP\_EPI0016 Revision 1 Reference: RWI\_WI\_EPI0005

Effective Date: 15Jun2018

Page 88 of 92

Objectives	Questions	Is the question included in the assessment of success? (Yes/No)	Definition of correctly answered question	Assessment of success
	Q7. Please specify the reasons you do not find the [patient card: name in the local language] useful?	No; complementary information on user friendliness of patient card		
	Q8. Please specify the reasons you do not always choose to inform the patient/caregiver about the [patient card: name in the local language]?	No; complementary information regarding informing patients about the patient card		
	Q9. Please select the option that best describes your experience with the outer packaging of methotrexate once weekly products	Yes	Question completed correctly [Answers '1' or '2' are desirable]	A pharmacist is successful for self-declared behaviour when the question regarding self-declared
Self-declared behaviour (2 questions)	Q10. Please specify the reasons you do not frequently/always mark the day of intake for once-weekly methotrexate prescriptions on the outer packaging (for oral formulations)?	No; complementary information related to Q8		behaviour is completed with desirable answers.  Success for self-declared behaviour if ≥80% of pharmacists are successful.

Template No.: RWI\_TP\_EPI0016 Revision 1 Reference: RWI\_WI\_EPI0005

Effective Date: 15Jun2018

Protocol/Study No: SC02 EMA/2018/19/PE Page 89 of 92

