## Assessment of success

In each of the 3 surveys, the proportion of correct or desirable responses across all questions related to the evaluation of the objectives of the surveys will be considered to assess the success.

Template No.: RWI\_TP\_EPI0016 Revision 1 Reference: RWI\_WI\_EPI0005

Protocol/Study No: SC02 EMA/2018/19/PE

Page 46 of 92

The questions considered as complementary will not be included in the assessment of success. The details of the assessment of the success for each survey and each objective is described in Annex 5.

Success at the prescriber, pharmacist, patient level will be defined for each objective based on the number of sub-questions related to that objective being answered correctly or desirably. It is proposed to set the threshold to at least 80% of knowledge questions, including sub-questions, are completed with correct/desirable answers. .

A threshold of 80% successful prescribers/pharmacists/patients on each of the outcomes of awareness, knowledge and self-declared behaviour (self-declared behaviour is not for patients) would be considered appropriate for assessing the effectiveness of RMM.

If additional information from published literature becomes available at the time of reporting, then the results will be discussed in the context of this new information. The methods of reporting and analysis of results obtained will be done as already described in the Protocol and will be further detailed in the SAP.

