# **ANNEX 5. ASSESSMENT OF SUCCESS**

# 5.1 Assessment of Success (Prescriber questionnaire)

Objectives	Questions	Is the question included in the assessment of success? (Yes/No)	Definition of correctly answered question	Assessment of success
	Q1. Please select the option that best describes your experience with the [Direct Healthcare Professional Communication (DHPC): country-specific name] distributed on [country-specific date of distribution] for methotrexate formulations?	Yes	Question completed correctly [Answer '1' or '2' is desirable]	A prescriber is successful for receipt and awareness when he/she receives the DHPC, the HCP guide, the HCP checklist (desirable answers) and is aware of the patient card (desirable answers).  Success for receipt and awareness if ≥80% of prescribers are successful
Receipt and Awareness (5 questions)	Q2. Please select the option that best describes your experience with the [HCP guide: country-specific name] distributed on [country-specific date of distribution]?	Yes	Question completed correctly [Answer '1' or '2' is desirable]	
	Q3. Please select the option that best describes your experience with the [HCP checklist: country-specific name] distributed on [country-specific date of distribution]?	Yes	Question completed correctly [Answer '1' or '2' is desirable]	
	Q4. Please select the option that best describes your experience with the [patient card: name in the local language] (for oral methotrexate formulations)?	Yes	Question completed correctly [Answer '1' or '2' or '3' is desirable]	

Template No.: RWI\_TP\_EPI0016 Revision 1 Reference: RWI\_WI\_EPI0005

Effective Date: 15Jun2018

Page 85 of 92

Objectives	Questions	Is the question included in the assessment of success? (Yes/No)	Definition of correctly answered question	Assessment of success
	Q5. In your daily practice, what version of the educational materials (EM) related to methotrexate do you use?	No; complementary information on mode of distribution		
Knowledge (1 question)	Q6. According to your knowledge about the conditions of use for methotrexate, please indicate if you agree or disagree with the following statements.	Yes	Question completed correctly (16 sub-questions [10 False and 6 True])	A prescriber is successful for knowledge when he/she scores at least 13 out of 16 points (80%) for sub-questions that are correctly answered.  Success for knowledge if ≥ 80% of prescribers are successful.

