Knowledge	Q8. According to your knowledge about the safety measures on the outer packaging of oral and parenteral methotrexate-containing products, please indicate if you agree or disagree with the following statements	Yes	Question completed correctly (4 sub-questions [2 False and 2 True])	
(13 questions)	Q9. Did your pharmacist write the weekday for intake in the respective box of the reminder on the methotrexate packaging?	No; complementary information on packaging reminder		
	Q10. According to your knowledge about the conditions of use for methotrexate, please indicate if you agree or disagree with the following statements.	Yes	Question completed correctly (6 sub-questions [3 False and 3 True])	
	Q11. According to your knowledge about methotrexate, which of the following symptoms are associated with methotrexate overdose?	Yes	Question completed correctly (9 sub-questions [2 False and 7 True])	

Template No.: RWI\_TP\_EPI0016 Revision 1 Reference: RWI\_WI\_EPI0005

Effective Date: 15Jun2018

Page 91 of 92

Q12. How did you gain an understanding about the dosing instructions for once weekly methotrexate?	No; complementary question on source of understanding about the dosing instructions	
Q13. How did you gain an understanding about the risks (side-effects, risk of overdose etc.) associated with taking methotrexate?	No; complementary question on source of understanding about the risks	
Q14. What helps you to remember to take methotrexate as a once-weekly dose?	No; complementary question on reminders set by patients	
Q15. How would you describe your experience with the [patient card: name in the local language]?	No; complementary information on user friendliness of patient card	
Q16. How would you describe your experience with the visual reminder for taking/using methotrexate/ noting down the day of the week to take methotrexate on the outer packaging?	No; complementary information on user friendliness of packaging	
Q17. How would you describe your experience with the information provided in the boxed warning in the methotrexate package leaflet?	No; complementary information on user	

Template No.: RWI\_TP\_EPI0016 Revision 1 Reference: RWI\_WI\_EPI0005

Effective Date: 15Jun2018

Page 92 of 92

	friendliness of packaging	-
Q18. According to your experience please indicate if you have ever accidently taken the once-weekly dose of methotrexate as a daily dose	No; complementary question on patient experience	

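### Annex 5.2 declares four sub-questions for pharmacist Q5 but keys five answers, so the key and the 8-of-10 knowledge cut-off must be reconciled before scoring

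*Protocol*

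**What the plan says.** Section 9.7.2.2 of the Protocol, under Assessment of success, sets the rule for the individual respondent: "It is proposed to set the threshold to at least 80% of knowledge questions, including sub-questions" must be answered correctly or desirably. It then sets the rule for the group: "A threshold of 80% successful prescribers/pharmacists/patients on each of the outcomes of awareness, knowledge and self-declared behaviour". It refers to Annex 5 for the details, so the Annex 5 tables are the operative scoring definitions.

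Annex 5.2 scores pharmacist knowledge on two questions.

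- Q4, on the patient card: "6 sub-questions; answers '1', '3' and '5' are True; '2', '4' and '6' are False".
- Q5, on the safety measures on the outer packaging: "4 sub-questions; answers '1' and '3' are True; '2' '4' and '5' are False".

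A pharmacist passes on knowledge when he or she "scores at least 8 out of 10 points (80%) for sub-questions that are correctely answered". The remaining questions in the knowledge block (Q6 to Q8) are marked complementary and are not scored. The pharmacist questionnaire itself is a stand-alone document (Annex 1) and is not reproduced in the Protocol.

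**The concern.** One bracket gives two different sizes for Q5. The pass mark depends on that size, because 10 points is the sum of the Q4 and Q5 items. If someone programs all five keyed answers and keeps a pass mark of 8, the effective requirement falls below the 80% that section 9.7.2.2 sets. If Q5 has only four items, the key refers to an item that does not exist.

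Pharmacist knowledge is one of the outcomes that answer primary objective 2. The item count also forms the denominator of the individual knowledge score in section 9.7.2.2, defined there as a proportion of correct responses. A count left open until answers are in hand would leave the success criterion open to choice after the fact. Section 6 plans data collection from 1 January to 30 April 2022, and this Protocol version is dated 21 February 2022, so the point should be settled promptly.

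**Working it through.** **Inputs from the documents**

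- Pharmacist Q4: 6 declared; 3 True + 3 False = 6 keyed. These agree.
- Pharmacist Q5: 4 declared; 2 True + 3 False = 5 keyed. These disagree.
- Pass mark: 8 of 10 points, labelled 80% (Annex 5.2).
- Individual threshold: at least 80% of knowledge items (section 9.7.2.2).
- Group threshold: at least 80% of pharmacists pass (section 9.7.2.2 and Annex 5.2).

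**Step 1. Reproduce the stated figure.** With the declared counts, 6 + 4 = 10 and 8/10 = 80.0%. The smallest integer at or above 0.8 × 10 is 8. The Protocol's figure reproduces.

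**Step 2. Use the keyed counts.** 6 + 5 = 11 and 8/11 = 72.7%, below 80%. Since 0.8 × 11 = 8.8, the rule needs 9 points, and 9/11 = 81.8%.

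**Step 3. Check whether the other surveys show the same mismatch.**

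- Prescriber Q6 (Annex 5.1): "16 sub-questions [10 False and 6 True", and 10 + 6 = 16. The pass mark of 13 is the smallest integer at or above 0.8 × 16 = 12.8; 13/16 = 81.25%. Consistent.
- Patients (Annex 5.3): Q7, Q8, Q10 and Q11 give 6 + 4 + 6 + 9 = 25, and 20/25 = 80%. Consistent.

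The mismatch is confined to pharmacist Q5.

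**Step 4. Weigh the two readings.** Three things favour four items: the declared count; the total of 10, which needs exactly four; and patient Q8, which has the same stem and is given as "4 sub-questions [2 False and 2 True". Removing item 5 from the pharmacist key leaves 1 and 3 True, 2 and 4 False. That is the same even split, and it follows the alternating pattern of Q4. Only the fifth keyed answer points the other way.

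**Step 5. Illustrate the size.** The Protocol gives no chance of a correct answer per item. Assume independent items with a common chance p. The chance that one pharmacist passes with at least k of n items is the binomial upper tail, the sum over x from k to n of C(n, x) p^x (1 − p)^(n − x).

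| p (assumed) | 8 of 10 | 8 of 11 | 9 of 11 |
|---|---|---|---|
| 0.70 | 38.3% | 57.0% | 31.3% |
| 0.80 | 67.8% | 83.9% | 61.7% |
| 0.90 | 93.0% | 98.1% | 91.0% |

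Solving for a pass chance of exactly 80% gives p = 0.783 for 8 of 11, 0.842 for 8 of 10 and 0.857 for 9 of 11. If Q5 has five items, the expected group verdict therefore differs between a pass mark of 8 and one of 9 only for p between about 0.78 and 0.86. At 0.70 all three rules fall short of 80%, and at 0.90 all three exceed it.

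**The case against.** The strongest reply is that this is a stray character with no numerical effect. If item 5 does not exist, nobody can score on it; the total stays at 10 and 8 of 10 meets the 80% rule exactly. The evidence in the Protocol favours this reading, and it may well be right. It cannot be confirmed from the Protocol, because the questionnaire is not part of it.

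A second reply is that section 9.7.2.2 already states the governing 80% rule, so a careful programmer would derive the right pass mark. That limits the harm but does not remove it: Annex 5.2 fixes a number of points as well as a percentage, and an analysis plan that copied the cell would carry the conflict forward.

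A third is that the scope is small. That stands. Knowledge is one of three pharmacist outcomes, alongside awareness and self-declared behaviour. The per-question percentages and the counts reaching 70%, 80%, 90% and 100% do not use the 8-of-10 pass mark, although they do need a correct key.

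A reader might infer that the plan's pharmacist threshold really is 72.7%, or that its arithmetic is wrong. The document does not support either. The stated sum is correct for the declared count, and 72.7% arises only if the questionnaire has five items and all five are scored against a pass mark written for ten points.

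**Conclusion.** Annex 5.2 is inconsistent as written for pharmacist Q5, and the count, the key and the pass mark cannot all be right. Four items is the better supported reading, under which the key is wrong by one entry and 8 of 10 stands. If there are five items, the pass mark is one point too low: 8/11 = 72.7% where at least 80% is required.

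It would be tempting to say that the slip moves pharmacist knowledge across the 80% success line. At an assumed 0.80 per item it would, from 61.7% at 9 of 11 to 83.9% at 8 of 11. But that needs the less supported five-item reading, an unchanged pass mark, and a per-item chance within about 0.78 to 0.86. The Protocol gives no item-level figure, and the calculation assumes independent items of equal difficulty, so it shows what is possible, not what to expect.

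This is a correction needed before responses are scored, and probably an editorial one. The prescriber and patient knowledge cut-offs are not affected.

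**What to change.** Compare Annex 5.2 with the stand-alone pharmacist questionnaire before any scoring.

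- If Q5 has four items, delete item 5 from the key, after confirming that the other four truth values match the questionnaire. Keep 8 of 10.
- If Q5 has five items, change the declared count to 5, the total to 11 and the pass mark to 9.

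In either case, state the pass mark in Annex 5.2 as the smallest integer at or above 80% of the scored items, so that it follows the final questionnaire. Carry the same count and key into the statistical analysis plan and the scoring program.

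The cost is one look at the questionnaire and one line of text. No data collection or sample size changes.
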